4.9.3 Secondary Efficacy Analysis

The secondary efficacy variables will be analyzed using the mITT, and the missing data will be handled using the MVTF, EM and LOCF methods:

- Change from baseline to day 3 in sputum viscosity score: the hypothesis of superiority of NAC compared to placebo will be assessed using the same nonparametric test (stratified Mann-Whitney U Statistics blocking for baseline score), whilst Hodges Lehmann point estimate of the median treatment differences together with associated two-sided 95% confidence intervals will be computed using nonparametric bootstrap.
- Change from baseline to day 3 in expectoration difficulty score: the hypothesis of superiority of NAC compared to placebo will be assessed using the same nonparametric test (stratified Mann-Whitney U Statistics blocking the baseline score), whilst Hodges Lehmann point estimate of the median treatment differences together with associated two-sided 95% confidence intervals will be computed using nonparametric bootstrap.
- Change from baseline to day 3 and to day 7 period in sputum color score: the hypothesis of superiority of NAC compared to placebo will be assessed using the same nonparametric test (stratified Mann-Whitney U Statistics blocking for baseline score), whilst Hodges Lehmann point estimate of the median treatment differences together with associated two-sided 95% confidence intervals will be computed using nonparametric bootstrap.

- Change from baseline to day 3 and to day 7 period in cough severity score: the hypothesis of superiority of NAC compared to placebo will be assessed using the same nonparametric test (stratified Mann-Whitney U Statistics blocking for baseline score), whilst Hodges Lehmann point estimates of the median treatment differences together with associated two-sided 95% confidence intervals will be computed using nonparametric bootstrap.
- Change from baseline to day 3 and to day 7 in sputum volume: the hypothesis of superiority of NAC compared to placebo will be assessed using the same nonparametric test (stratified Mann-Whitney U Statistics blocking for baseline score), whilst Hodges Lehmann point estimate of the median treatment differences together with associated two-sided 95% confidence intervals will be computed using nonparametric bootstrap.

The same statistical analysis (stratified Mann-Whitney U Statistics blocking for baseline score) will be carried out for testing superiority of ambroxol vs. placebo on the same efficacy endpoints. Results will be used for the purpose of verifying study's assay sensitivity.

The following summaries will be provided using the mITT population (Section 4.4.3):

- A summary of comparing ambroxol and placebo for the change from baseline to day 3 and to day 7 in sputum viscosity score, in which the missing data will be handled using the MVT, expectation-maximization (EM) algorithm and last observation carried forward (LOCF) as sensitivity analyses.
- A summary of comparing ambroxol and placebo for the change from baseline to day 3 and to day 7 in expectoration difficulty score, in which the missing data will be handled using the MVT, expectation-maximization (EM) algorithm and last observation carried forward (LOCF) as sensitivity analyses.
- A summary of comparing ambroxol and placebo for the change from baseline to day 3 and to day 7 in sputum color score, in which the missing data will be handled using the MVT, expectation-maximization (EM) algorithm and last observation carried forward (LOCF) as sensitivity analyses.
- A summary of comparing ambroxol and placebo for the change from baseline to day 3 and to day 7 in cough severity score, in which the missing data will be handled using the MVT, expectation-maximization (EM) algorithm and last observation carried forward (LOCF) as sensitivity analyses.
- A summary of comparing ambroxol and placebo for the change from baseline to day 3 and to day 7 in sputum volume, in which the missing data will be handled using the MVT, expectation-maximization (EM) algorithm and last observation carried forward (LOCF) as sensitivity analyses.

The stratified Mann-Whitney U test statistic can be seen in the Appendix (Section 4.14.5).

4.9.4 Multi-center Analysis

CCI In the first instance, since the aim of the analysis is to examine sites, the analysis will be performed using individual

sites (i.e. no pooling of sites). If the situation occurs where there are convergence issues or SAS errors/warnings due to some sites with small numbers of subjects, sites with 8 or fewer randomized subjects will be grouped for the multi-center analysis.

The following summaries will be provided for each co-primary efficacy endpoint:

- A summary of the change from baseline to day 7 in sputum viscosity score using the mITT population, in which the missing data will be handled using the MVTF. Two-way non-parametric ANOVA will be performed by including treatment, site, and site-by-treatment interaction terms in the model.
- A summary of the change from baseline to day 7 in expectoration difficulty score using the mITT population, in which the missing data will be handled using the MVTF. Two-way non-parametric ANOVA will be performed by including treatment, site, and site-by-treatment interaction terms in the model.

Forest plots will be generated to display the results at each center. Note that the Forest plots utilize a GLM fit to the ranked datasets used by the two-way non-parametric ANOVA. This is because it is not possible to include an interaction term (site-by-treatment) into the stratified Mann-Whitney U Statistic test utilized for analysis of the co-primary endpoints. Caution must be taken in interpreting the results of the multi-center analysis owing to difference in statistical methodology compared to the primary and secondary endpoints analysis as well as a lack of appropriate stratification for the randomization.

4.10 Safety Evaluation

All safety summaries and listings will be based upon the Safety Population (Section 4.4.4).

4.10.1 Extent of Exposure

Exposure will be summarized both in terms of the treatment duration (in days) and the total dose administered up to the end of the last administration of IMP, as recorded on the eCRF. The duration of treatment will be calculated from the first administration date to the last administration date at the end of the last administration of treatment arm (duration = the last administration date - the first administration date +1). The total dose of the treatment arm will be the summation of actual administration dose at every administration.

Investigator will assess adherence with IMP dosing regimen on an ongoing basis by determining the amount of IMP dispensed, used (i.e. returned open ampoules/vials) and the amount of IMP returned (i.e. returned, unopened ampoules/vials) at Visit 2 (first dose), Visit 3 and Visit 4 (end of treatment) or unscheduled Deterioration Visit/premature discontinuation visit.

The evaluation of compliance will be done using the following formula:

$$\% \text{ of administered drug} = 100 \times \frac{\text{Total number of administered doses}}{\text{Total number of scheduled doses}}$$

The compliance calculation will be based on visit basis. For example, if subject takes IMP only in the morning but withdraws in the afternoon without taking IMP as planned, then the total number of scheduled doses at this visit will count two doses in the denominator.

A subject would be considered as compliant if % of administered drug is at least 80%.

The following summaries will be provided:

- A summary of the duration and the actual total dose by treatment group
- A summary of number and percentage of subjects with treatment compliance by treatment group and visit.

The following listings will be provided:

- A by-subject listing of administration of IMP
- A by-subject listing of treatment compliance

4.10.2 Adverse Events

An AE is "any untoward medical occurrence in a patient or clinical trial subject administered a medicinal product and which does not necessarily have a causal relationship with this treatment".

Adverse events will be coded using Medical Dictionary for Regulatory Activities (MedDRA) Version 23.1.

Any AE occurring onset date on or after the date of the first IMP administration, i.e. Visit 2, until the end of the trial, i.e. follow-up phone call, will be considered as a treatment emergent AE (TEAE). AEs which are already present before the first IP and increase in severity after the first IP will be considered as TEAEs. Pre-existing AEs before the first IP with no increase in severity after the first IP will not be considered as TEAEs. A Pre-treatment AE will be defined as any AE with an onset date before the date of first administration of IMP.

Imputation of partial dates of AE record is described in Appendix 4.14 (section 4.14.7).

Following summaries will be provided:

- An overview of all TEAEs including any TEAEs with relationship to IMP, any TEAEs leading to drug withdrawn, any TEAEs leading to drug interrupted, any TEAEs leading to fatal, any TEAEs of Covid-19, by treatment group.
- A summary of Pre-treatment Adverse Events by SOC, PT and CTCAE Grade (Safety Set)
- A summary of the number and percentage of subjects reporting an TEAE and the number of TEAEs, by treatment group, SOC, and PT
- A summary of the number and percentage of subjects reporting a TEAE with Incidence $\geq 5\%$ of Patients by treatment group, SOC, and PT
- A summary of the number and percentage of subjects reporting Other adverse events with Incidence $\geq 5\%$ of Patients by treatment group, SOC, and PT
- A summary of the number and percentage of subjects reporting a TEAE Related to IMP by treatment group, SOC, and PT

- A summary of the number and percentage of subjects reporting an TEAE and the number of TEAEs, by treatment group, relationship, SOC, and PT
- A summary of the number and percentage of subjects reporting an TEAE and the number of TEAEs, by treatment group, severity, SOC, and PT
- A summary of the number and percentage of subjects reporting a TEAE Leading to Study Discontinuation by treatment group, SOC, and PT
- A summary of the number and percentage of subjects reporting a TEAE Leading to Drug withdrawal of IMP by treatment group, SOC, and PT

For the summarization of number of subjects, a subject will be counted only once for each SOC and each PT, even if the subject reported one or more event under each subcategory; for the summarization of number of events, the number of TEAEs will count all TEAEs of each subject under each SOC and each PT.

For each TEAE, the most extreme grade recorded in eCRF will be attributed and used in the by-severity summaries. If the severity is missing, it will be imputed as the most extreme case, i.e., Severe. If relationship to study treatment is missing, the relationship will be imputed as Related.

Unless specified otherwise, the table of a summary will be ordered in terms of decreasing number of subjects for system organ class and then preferred term within system organ class in the overall group, and then alphabetically for SOC and PT within SOC if the frequency is tied.

A by-subject listing of all AEs will be provided.

4.10.3 Deaths and Serious Adverse Events

Any SAE occurring from the day of the first IMP administration, i.e. Visit 2, until the end of the trial, i.e. follow-up phone call, will be considered as a treatment-emergent SAE.

Following summaries will be provided:

- An overview of all treatment-emergent SAEs including any treatment-emergent SAEs with relationship to IMP, any treatment-emergent SAEs leading to drug withdrawn, any treatment-emergent SAEs leading to drug interrupted, any treatment-emergent SAEs leading to death, any treatment-emergent SAEs of Covid-19, by treatment arm.
- A Summary of Death
- A summary of the TEAE Leading to Death by System Organ Class, Preferred Term
- A summary of the number and percentage of subjects reporting a SAE and the number of SAEs, by treatment group, SOC and PT
- A summary of the number and percentage of subjects reporting a treatment-emergent SAE and the number of treatment-emergent SAEs, by treatment group, SOC and PT
- A summary of the number and percentage of subjects reporting a treatment-emergent SAE Related to IMP, by treatment group, SOC, and PT

- A summary of the number and percentage of subjects reporting a treatment-emergent SAE and the number of treatment-emergent SAEs, by treatment group, severity (mild, moderate, severe), SOC, and PT
- A summary of the number and percentage of subjects reporting a treatment-emergent SAE and the number of treatment-emergent SAEs, by treatment group, relationship, SOC, and PT
- A summary of the number and percentage of subjects reporting a treatment-emergent SAE leading to drug withdrawal, by treatment group, SOC and PT
- A summary of the number and percentage of subjects reporting a treatment-emergent SAE leading to Study discontinuation, by treatment group, SOC and PT

Tables should follow the similar format described for TEAEs if appropriate.

A by-subject listing of all SAEs will be provided.

4.10.4 Laboratory Evaluations

Laboratory evaluations will include Hematology, Clinical Chemistry (biochemistry), and Pregnancy test. Lab value will be converted to standard unit.

Quantitative laboratory measurements reported as '< X', i.e. below the lower limit of quantification (BLQ), or '> X', i.e. above the upper limit of quantification (ULQ), will be converted to X for the purpose of quantitative summaries, but will be presented as recorded, i.e. as '< X' or '> X' in the listings.

The evaluations of hematology and clinical chemistry (biochemistry) will be performed at Screening Visit (Visit 1) and Visit 4 and in case of premature discontinuation.

A dipstick urine pregnancy test for women of childbearing potential will be performed at Randomization Visit (Visit 2) and at Visit 4 and/or at unscheduled deterioration visit/premature discontinuation visit.

The parameters of hematology, clinical chemistry(biochemistry) and pregnancy test are presented in the following table.

Hematology:			
Hematocrit	Hemoglobin	Platelet count	Neutrophils
Lymphocytes			
Eosinophils	Basophils		
Clinical Chemistry(biochemistry):			
BUN	Chloride	AST	
Creatinine	Uric acid	ALT	
Sodium	Amylase	γGT	
Potassium	ALP	Bilirubin (direct and total)	
Calcium	UREA		
Pregnancy Test:			
Urine β-hCG (dipstick)			

The following summaries will be provided:

- A summary of hematology observed values at Visit 1 and Visit 4, and the changes from Visit 1 for each laboratory parameter by treatment group
For the continuous parameters, it will be summarized using the descriptive statistics. For the categorical parameters, a shift table of the test results at Visit 4 compared to the test results at Visit 1 will be provided
- A summary of clinical chemistry (biochemistry) observed values at Visit 1 and Visit 4, and the changes from Visit 1 for each laboratory parameter by treatment group
- A summary of urine Pregnancy Test observed values at Visit 1 and Visit 4
- A shift table of the pregnancy test results at Visit 4 compared to the pregnancy test results at Visit 2
- Summary of subjects with values outside central laboratory normal range by visit for each treatment group (Safety Population)

The following listings will be provided:

- A by-subject listing of all laboratory data, in which all values appearing outside the laboratory normal range will be highlighted
- A by-subject list of pregnancy test results

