10.11. PREMATURE DISCONTINUATION VISIT

In case of premature discontinuation for any other reasons than those listed in 10.10 all evaluations requested at Visit 4 should be performed, excluding study medication administration.

A premature discontinuation visit must also be conducted in case of unexpected pregnancy.

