11.1.4. LABORATORY EVALUATIONS

Routine laboratory evaluations will be performed at Screening Visit (Visit 1) and Visit 4 and in case of premature discontinuation.

The blood samples must be collected after the 12-lead ECG has been performed.

The haematology and clinical chemistry parameters detailed in Table 1 will be analysed by the local hospital laboratory.

Subjects with clinically relevant impaired renal function, as defined by serum creatinine levels ≥ 3.0 x upper limit of normal at Visit 1 will not be randomized.

Subjects with clinically relevant impaired liver function, as defined by serum ALT and/or AST ≥ 3.0 x upper limit of normal at Visit 1 will not be randomized.

A dipstick urine pregnancy test for women of childbearing potential will be performed at Randomization Visit (Visit 2) and at Visit 4 and/or at unscheduled deterioration visit/premature discontinuation visit.

Female subjects who become pregnant during the trial must be withdrawn from the trial without delay and undergo the premature discontinuation visit; these patients are to be followed up to determine the outcome of the pregnancy. The Investigator is required to inform the Sponsor of a subject's pregnancy and the estimated date of delivery. Reporting requirements are outlined in [Section 18.10](#).

Clinical laboratory tests will be reviewed for results of potential clinical significance before Visit 2 to confirm patient's eligibility and during the trial, as appropriate. Clinically significant laboratory abnormalities arising at Visit 4 (or at premature discontinuation visit) are considered AEs. Where possible, a diagnosis should be ascribed to the abnormal lab test.

Table 1 CLINICAL LABORATORY EVALUATIONS

Hematology: at Screening Visit (Visit 1) and Visit 4 or premature discontinuation visit			
Hematocrit	Hemoglobin	Platelet count	Red blood cell count
White blood cell count and differential (neutrophils, lymphocytes, monocytes, eosinophils and basophils)			
Clinical Chemistry: at Screening Visit (Visit 1) and visit 4 or premature discontinuation visit			
BUN or UREA	Chloride	AST	
Creatinine	Uric acid	ALT	
Sodium	Amylase	γGT	
Potassium	ALP	Bilirubin (direct and total)	
Calcium			
Pregnancy Test: at Screening Visit (Visit 1), Visit 4 or premature discontinuation visit			
Urine β-hCG (dipstick)			

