For 24-hour sputum collection, the baseline measurement will be the last available data captured on Visit 2 (Day 1) or the next day (Day 2). This is because the collection of sputum is to begin on Day 1 and lasts for 24 hours up until the same time the next day (Day 2). Therefore, the baseline sputum volume measurement may be after the first dose of IMP.

Scheduled and Unscheduled Assessments

The by-visit tables will only include the scheduled assessments, unless specifically stated otherwise. If more than one value is available for a given visit, the first valid observation will be used in summary tables, unless specifically stated otherwise, and all observations will be presented in listings.

Unscheduled assessments will be included in listings, but not in summary tables.

Detection of Outliers

Any outliers that are detected during the review of the data before database lock will be investigated. If necessary, queries will be issued to Investigators, to either correct or confirm the outlier.

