4.10.5 Vital Signs and Physical Examination

Vital Signs

Vital Signs will be assessed at Screening Visit (Visit 1), Randomization Visit (Visit 2), Visit 3 and Visit 4 and/or at the unscheduled deterioration visit/premature discontinuation.

Vital signs include:

- heart rate (beats/minute),

- systolic and diastolic blood pressure, measured after at least 5 minutes in the supine position (mmHg)
- respiration rate (breaths/min)
- body temperature, measured under the arm pit (°C)

A summary of the observed values and changes from Visit 1 for each vital sign by treatment group and overall at each visit will be provided. Both raw values and changes from Visit 1 will be summarized using descriptive statistics.

A by-subject listing of vital signs will be provided.

Physical Examination

At Visit 1, Visit 2, Visit 3 and Visit 4, and/or at the unscheduled deterioration Visit/premature discontinuation, a physical examination of general body systems will be performed according to current medical standards and site practice. The general body systems include:

- Respiratory System
- Cardiovascular System
- Abdomen
- General Appearance
- Head and Neck
- Lymph Nodes
- Musculoskeletal System
- Nervous System
- Skin
- Endocrine System
- Ears, nose and throat
- Hematopoietic System
- Reproductive System
- Urinary System

The examination is to include a chest auscultation.

A summary of the number and percentage of subjects for each body system by category (normal, abnormal not clinically significant, and abnormal clinically significant), treatment group and overall at each visit will be provided.

A by-subject listing of physical examination will be provided.

4.10.6 12-Lead Electrocardiogram

12-lead electrocardiogram (ECG) recordings will be obtained at each study center using site machines at the Screening Visit (Visit 1) to verify the eligibility of the subject, and at Visit 4 or unscheduled deterioration visit.

ECG will be performed after obtaining vital signs. Prior to recording, the subject should be at rest for at least 5 mins.

ECG will be evaluated by the investigator/local medical staff and the recording will be reported in the eCRF as “normal”, “abnormal clinically significant” or “abnormal not clinically significant”.

A shift table of the ECG assessments at Visit 4 compared to the ECG assessments at Visit 1 by treatment group will be provided. When there are multiple assessments of ECG taken at a visit, the worst ECG finding will be used.

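### Laboratory and ECG tables compare Visit 1 with Visit 4 and no rule says where early stoppers' tests go; the out-of-range table also names a central laboratory range although samples are analysed locally

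*SAP*

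**What the plan says.** **Tests at early stopping.** Protocol 10.11 states that at premature discontinuation "all evaluations requested at Visit 4 should be performed, excluding study medication administration". Visit 4 includes blood sampling and a 12-lead ECG. Protocol 10.10 asks for the full Visit 4 evaluations when a patient stops at a deterioration visit, and has an ECG done at that visit in any case. The flow chart in Appendix 1 gives premature discontinuation its own column, apart from Visit 4, with blood sample and ECG marked. SAP 4.10.4 acknowledges the schedule: haematology and chemistry "will be performed at Screening Visit (Visit 1) and Visit 4 and in case of premature discontinuation".

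**Tables.** SAP 4.10.4 then plans "A summary of hematology observed values at Visit 1 and Visit 4, and the changes from Visit 1 for each laboratory parameter by treatment group" and "A summary of clinical chemistry (biochemistry) observed values at Visit 1 and Visit 4, and the changes from Visit 1". Categorical laboratory parameters get a shift table of Visit 4 against Visit 1. SAP 4.10.6 says "A shift table of the ECG assessments at Visit 4 compared to the ECG assessments at Visit 1 by treatment group will be provided". SAP 4.2 restricts by-visit tables to scheduled assessments unless stated otherwise, and adds: "Unscheduled assessments will be included in listings, but not in summary tables".

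**Reference range.** SAP 4.10.4 lists "Summary of subjects with values outside central laboratory normal range by visit for each treatment group". Protocol 20.4.8 also refers to a central laboratory range. Protocol 11.1.4 says that the samples "will be analysed by the local hospital laboratory".

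**The concern.** A patient who stops before day 7 has no Visit 4. The protocol collects an end-of-treatment blood sample and ECG from that patient at another visit, and the SAP does not say which table column, if any, receives the result. For efficacy the question is answered: SAP 4.9.1.3 expressly brings premature-discontinuation measurements into the imputation. There is no counterpart for safety.

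The trial has a stated safety objective, and the laboratory and ECG tables are where the arms are compared on these measurements. Patients who stop early may differ from completers, so a table confined to Visit 4 may not describe everyone treated.

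The range wording is a separate defect. The table is to be built against a range from a central laboratory that neither document describes, so it cannot be programmed without a choice that the plan does not record.

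**Working it through.** **1. Size of the group affected.** Inputs from protocol 20.3 and SAP 4.11: 100 evaluable patients per arm, drop-out about 10%, 111 randomised per arm, 333 in total.

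The plan's own figure: 100 / (1 − 0.10) = 111.1 per arm. The stated 111 and 333 are reproduced.

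Patients without a Visit 4 = 111 × drop-out rate per arm, and 333 × drop-out rate in total:

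| Drop-out | Per arm | Total |
|---|---|---|
| 5% (assumed) | 5.6 | 16.7 |
| 10% (planned) | 11.1 | 33.3 |
| 15% (assumed) | 16.7 | 50.0 |

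These are upper bounds on what a mapping rule would recover, because some early stoppers will have no exit tests.

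**2. Where the results go.** Following an early stopper's blood sample and ECG through the SAP:

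- Laboratory summary, change and shift tables (4.10.4): defined on Visits 1 and 4, so no place is given.
- ECG shift table (4.10.6): defined on Visits 1 and 4, so no place is given.
- Out-of-range table (4.10.4): by visit and not expressly limited to Visits 1 and 4, so a separate discontinuation column is conceivable.
- By-subject listings (4.10.4, 4.10.6): included.
- Adverse event tables (4.10.2): included if judged clinically significant. Protocol 11.1.4 makes such laboratory findings at the discontinuation visit adverse events. Protocol 11.1.6 does so for ECG findings at the deterioration or discontinuation visit, unless related to a condition predating consent.

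**3. Effect on the displayed rate.** The documents give no abnormality rates, so those below are assumptions. Let d be the drop-out rate, pc the rate in completers and ps the rate in early stoppers. A Visit 4-only table shows pc. The rate in all patients is (1 − d)·pc + d·ps, and the share of affected patients absent from the table is d·ps divided by that rate. With d = 0.10 and pc = 3%:

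- ps = 3%: 0.9 × 3% + 0.1 × 3% = 3.0%. Shown 3.0%, so no distortion. The absent share is 0.3/3.0 = 10%, the same as the share of patients absent.
- ps = 10%: 0.9 × 3% + 0.1 × 10% = 3.7%. Shown 3.0%; absent share 1.0/3.7 = 27%.
- ps = 30%: 0.9 × 3% + 0.1 × 30% = 5.7%. Shown 3.0%; absent share 3.0/5.7 = 53%.

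For pc = 3% and ps = 10%, the absent share is 15% at 5% drop-out and 37% at 15% drop-out. The result depends on ps, which the documents do not give.

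**4. Reference range.** Protocol 11.1.4 assigns the analysis to local hospital laboratories, and protocol 19.5 names local laboratories among the data processors. SAP 3.1 plans about 25 sites. Against this, SAP 4.10.4 and protocol 20.4.8 cite a central range for the table, while the listing rule in each flags values against the laboratory's normal range, without the word central. Table and listing therefore do not name the same standard.

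**The case against.** The strongest reply is that the exclusion is inferred. SAP 4.2 sends unscheduled assessments to listings, but the premature-discontinuation visit is protocol-defined and is not labelled unscheduled; only the deterioration visit is. If the eCRF filed discontinuation data under Visit 4, they would enter the tables. This stands in part: the defect is a missing rule, not a stated exclusion. But neither document describes such filing, and the flow chart keeps the two visits apart.

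The second reply is that clinically important results are not lost. This stands. Significant abnormalities become adverse events, tabulated by arm with separate tables for events leading to drug withdrawal and to study discontinuation, and the listings hold everything. What remains is the descriptive change and shift information, and values that the investigator did not judge significant.

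Three stronger readings are tempting, and the documents do not support them:

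- A reader might infer that the safety tables are biased towards normal. That requires a higher abnormality rate in early stoppers, which no document gives. Early stoppers include patients discharged before day 7 (protocol 11.1.5), who need not be sicker. No difference between arms is shown either.
- A reader might infer that one range will be applied across about 25 laboratories and misclassify values. Neither document says so. The wording names a range that has no described source, and nothing more.
- A reader might infer that taking vital-sign change from Visit 1 contradicts the baseline definition in SAP 4.2. That definition is introduced as the general case, SAP 4.10.5 specifically sets change from Visit 1, and Visit 2 values are tabulated as well.

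**Conclusion.** The point holds as a gap in two safety reporting rules. No provision places early stoppers' end-of-treatment laboratory and ECG results in the laboratory summary, change and shift tables or the ECG shift table. The number concerned rests on the plan's own drop-out assumption and on the further assumption that every early stopper has the exit tests. The size and direction of any effect on the displayed rates cannot be determined from the documents.

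The central-range wording contradicts the local analysis of samples, and it does so in both documents.

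The primary analysis, the multiplicity control and the sample size are untouched.

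**What to change.** - In SAP 4.10.4 and 4.10.6, define end of treatment as Visit 4 or, if not done, the premature-discontinuation or deterioration visit, and state the order of preference for a patient who has both. Use this value in the change, shift and out-of-range tables, and say that it overrides the default in SAP 4.2.
- In SAP 4.10.4 and protocol 20.4.8, replace the central laboratory range with the reporting laboratory's own reference range, so that table and listing use one standard.

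The cost is SAP and protocol wording plus one visit-mapping line in the programming. The protocol already requires the tests, and flagging out-of-range values in the listing already calls for reference ranges.
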